**Table 2. Analysis Windows for EASI, SCORAD, IGA, BSA, PGIS, Laboratory Parameters, and Vital Sign Variables (Period 1)**

Scheduled Week	Nominal Day	P1 Rx Day Interval
Baseline	1	$\leq 1$
Week 2	15	2 – 22
Week 4	29	23 – 43
Week 8	57	44 – 71
Week 12	85	72 – 99
Week 16	113	100 – 126 a

a. Minimum of the upper bound and the day of the first dose in Period 2.

**Table 3. Analysis Windows for Pruritus NRS, ADerm-SS, ADerm-IS, and Actigraphy (Period 1)**

Scheduled Week	Nominal Day	P1 Rx Day Interval
Baseline	-1	< 1 a
Week 1	8	2 – 11
Week 2	15	12 – 18
Week 3	22	19 – 25
Week 4	29	26 – 32
Week 5	36	33 – 39
Week 6	43	40 – 46
Week 7	50	47 – 53
Week 8	57	54 – 60
Week 9	64	61 – 67
Week 10	71	68 – 74
Week 11	78	75 – 81
Week 12	85	82 – 88
Week 13	92	89 – 95
Week 14	99	96 – 102
Week 15	106	103 – 109
Week 16	113	110 – 116 b

- a. ADerm-IS **CCI** assessments collected on or before Day 1 will be used as baseline (P1 Rx Day Interval:  $\leq 1$ ).
- b. Minimum of the upper bound and the day of the first dose in Period 2 for efficacy analyses.

**Table 4. Analysis Windows for DLQI, MOS, and POEM (Period 1)**

Scheduled Week	Nominal Day	P1 Rx Day Interval
Baseline	1	$\leq 1$
Week 4	29	2 – 71
Week 16	113	72 – 154 a

- a. Minimum of the upper bound and the day of the first dose in Period 2.

**Table 5. Analysis Windows for Asthma Symptoms Questionnaire and Daytime Nasal Symptoms Questionnaire (Period 1)**

Scheduled Week	Nominal Day	P1 Rx Day Interval
Baseline	1	$\leq 1$
Week 16	113	2 – 224 a

a. Minimum of the upper bound and the day of the first dose in Period 2.

**Table 6. Analysis Windows for Blood Sample Parameters\* (Period 1)**

Scheduled Week	Nominal Day	P1 Rx Day Interval
Baseline	1	$\leq 1$
Week 8	57	2 – 85
Week 16	113	86 – 140 a

\* Including T (CD4+ and CD8+) cells, B (CD19+) cells, natural killer (NK) cells, and natural killer-T (NKT) cells.

a. Minimum of the upper bound and the day of the first dose in Period 2.

**Table 7. Analysis Windows for EASI, SCORAD, IGA, BSA, PGIS, Laboratory Parameters and Vital Sign Variables (Period 2)**

Scheduled Week	Nominal Day	P2 Rx Day Interval
Entry of Period 2 (Week 16)	1	$\leq 1$
Week 20	29	2 – 43
Week 24	57	44 – 85
Week 32	113	86 – 141
Week 40	169	156 – 211
Week 52	253	212 – 295
Week 64	337	296 – 379
Week 76	421	378 – 463
Week 88	505	464 – 546

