Note 1: Visit window is ± 3 days for Period 1 (Weeks 2, 4, 8, 12 and 16) and ± 5 days for Period 2 (Weeks 20, 24, 32, 40, 52, 64, 76 and 88) and a visit 4 weeks following topical rescue if applicable. Any of the procedures may be performed at the discretion of the investigator. Subjects who choose to discontinue study drug treatment, but continue to participate in the study, should complete a Premature Discontinuation Visit (PD Visit) as soon as possible, preferably within 2 weeks. Afterwards, subjects should follow the regular visit schedule and adhere to all study procedures except for dispensing study drug, PK sample collection, and blood and skin sample collection for exploratory research and validation studies. In addition, all future rescue and efficacy-driven discontinuation criteria no longer apply.

Note 2: Twice daily use of an additive-free, bland emollient is required for at least 7 days prior to Baseline and during the study.

Table 3. Study Activities – Optional and Mandatory Samples for Exploratory Research and Validation Studies

Activity	Screening D -30 to D -1	BL	Wk 2	Wk 4	Wk 8	Wk 12	Wk 16	Wk 20	Wk 24	Wk 32	Wk 40	Every 12 Weeks or PD ^a D365 – D617	4 Weeks Post Topical Rescue Visit	30- Day F/U Visit
Pharmacogenetic samples ^a		X												
Epigenetic samples ^a		X	X	X			X	X						
Transcriptomic and epigenetic samples ^a		X	X	X			X	X						
Plasma samples for analyses including, but not limited to, proteomic and targeted protein investigations ^a		X	X	X			X	X						
Serum samples for analyses including, but not limited to, proteomic and targeted protein investigations ^a		X	X	X			X	X						
Sample for PBMC assays ^a		X		X			X							
Skin Biopsies for analyses including, but not limited to, epigenetics, transcriptomics, proteomics, immunohistochemistry ^{a,b} and targeted investigations		X		X			X							

BL = Baseline Visit; D = Day; F/U = Follow-Up; PBMC = Peripheral Blood Mononuclear Cell; PD = Premature Discontinuation; Wk = Week

- Based on the value of the different technologies, samples may also be used to assess other biomarker signatures, including but not limited to metabolomics, lipidomics, and other approaches. Samples may be used for assay of study drugs if needed.

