### **Definition of Analysis Windows**

All time points and corresponding time windows in Periods 1 and 2 are defined based on P1 Rx Days P1 and P2 Rx Day, respectively.

Analysis time windows are constructed using the following algorithm:

- Determine the nominal Rx Day for each scheduled visit (e.g., Week 4 [4 weeks after baseline visit] equals P1 Rx Day 29).
- In order to include all post baseline data, the first post-baseline interval starts on the first day after the first dose of study drug (P1 or P2 Rx Day 2).
- Determine the window around a specific nominal Rx Day by adding or subtracting half of the interval between adjacent visits (e.g., days between Week 2 and Week 4 is 14). The threshold between adjacent visits is determined by splitting the interval evenly between the visits. If the resulting split is between Rx days, then the threshold is determined as the midpoint between the adjacent visits. If the resulting split is on an Rx day, then the threshold is determined as being between that Rx day and the Rx day prior to it (e.g., the split between Week 2 and Week 4 would be between P1 Rx Days 22 and 23).
- If more than one assessment is included in a time window, the assessment closest to the nominal day will be used. If there are two observations equidistant to the nominal day, the one after the nominal day will be used in analyses. If more than one assessment is included on the same day, then the worst assessment on that day will be used in analyses, except otherwise specified.

For subjects randomized but not dosed, Rx Day calculated relative to Randomization in each period.

For the efficacy variables, vital signs, and laboratory values, visit windows are defined as follows.

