**Table 8. Analysis Windows for Daily Pruritus NRS, ADerm-SS, and ADerm-IS (Period 2)**

Scheduled Week	Nominal Day	P2 Rx Day Interval
Entry of Period 2 (Week 16)	1	< 1 a
Week 17	8	2 – 11
Week 18	15	12 – 18
Week 19	22	19 – 25
Week 20	29	26 – 32
Week 21	36	33 – 39
Week 22	43	40 – 46
Week 23	50	47 – 53
Week 24	57	54 – 60
Week 25	64	61 – 67
Week 26	71	68 – 74
Week 27	78	75 – 81
Week 28	85	82 – 88
Week 29	92	89 – 95
Week 30	99	96 – 102
Week 31	106	103 – 109
Week 32	113	110 – 116
Week 33	120	117 – 123
Week 34	127	124 – 130
Week 35	134	131 – 137
Week 36	141	138 – 144
Week 37	148	145 – 151
Week 38	155	152 – 158
Week 39	162	159 – 165
Week 40	169	166 – 211
Week 52	253	212 – 295
Week 64	337	296 – 379
Week 76	421	380 – 463
Week 88	505	464 – 546

a. ADerm-IS CCI assessments collected on or before Day 1 of Period 2 will be used as entry of Period 2 (P2 Rx Day Interval:  $\leq 1$ ).

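### SAP Table 7 leaves Period 2 days 142–155 in no visit window and puts days 378–379 in two, against the SAP's own midpoint rule (wrong as written, limited impact)

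*SAP*

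**What the plan says.** SAP section 6.0 (Definition of Analysis Windows) states the rule: "The threshold between adjacent visits is determined by splitting the interval evenly between the visits". Where the midpoint falls on a study day, the text puts the boundary between that day and the day before. Its illustration does the opposite: "the split between Week 2 and Week 4 would be between P1 Rx Days 22 and 23". Day 22 is itself the midpoint, so the example gives the split day to the earlier visit. If a window holds several assessments, the one closest to the nominal day is used.

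The relevant rows, each giving visit, nominal day and interval in days from the first Period 2 dose, are:

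- Table 7: "Week 32 113 86 – 141", followed by "Week 40 169 156 – 211".
- Table 7: "Week 64 337 296 – 379", followed by "Week 76 421 378 – 463".
- Table 8, same visit: "Week 76 421 380 – 463". Tables 9 and 10 print 378 as Table 7 does.

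Table 7 governs EASI, SCORAD, IGA, BSA, PGIS, laboratory parameters and vital signs. Protocol Table 2, Note 1 allows ±5 days around Period 2 visits and also names "a visit 4 weeks following topical rescue if applicable". A premature-discontinuation visit has no fixed day: it follows the stopping of study drug, preferably within 2 weeks.

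**The concern.** A midpoint rule yields windows that touch without overlapping, so every post-baseline day maps to exactly one visit. Table 7 breaks this twice. A measurement on days 142–155 has no visit to be reported under. One on days 378–379 can be reported under two, and the closest-to-nominal rule does not settle this because it chooses between assessments within a window, not between windows for one assessment.

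At stake is whether the Period 2 by-visit tables are complete and reproducible. Two programmers following this SAP could produce different Week 40, 64 and 76 results. Any loss would fall mainly on subjects who stop treatment and leave, because their visits are the ones not tied to the schedule.

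**Working it through.** **Inputs.** Table 7 nominal days are 29, 57, 113, 169, 253, 337, 421 and 505 for Weeks 20, 24, 32, 40, 52, 64, 76 and 88. The boundary is (earlier nominal day + later nominal day) / 2. By the worked example the split day goes to the earlier visit: (15 + 29)/2 = 22, so the boundary is 22/23.

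**Rebuilding Table 7.**

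| Visits | Midpoint | Later window should start | Table 7 start |
|---|---|---|---|
| 20/24 | (29+57)/2 = 43 | 44 | 44 |
| 24/32 | (57+113)/2 = 85 | 86 | 86 |
| 32/40 | (113+169)/2 = 141 | 142 | **156** |
| 40/52 | (169+253)/2 = 211 | 212 | 212 |
| 52/64 | (253+337)/2 = 295 | 296 | 296 |
| 64/76 | (337+421)/2 = 379 | 380 | **378** |
| 76/88 | (421+505)/2 = 463 | 464 | 464 |

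All interior upper bounds reproduce, and all starts except Week 40 and Week 76. The final upper bound is 546, against 505 + 42 = 547; it separates no two visits and creates neither a gap nor an overlap. Under the literal tie wording the two starts would be 141 and 379, so neither reading gives 156 or 378.

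**Size.** The gap is days 142 to 155: 155 − 142 + 1 = 14 days. The overlap is days 378 and 379. Table 8 has neither; Tables 9 and 10 have the overlap only.

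**Which visits can land there.**

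- Scheduled visits (±5 days): Week 32 on days 108–118, Week 40 on 164–174, Week 64 on 332–342, Week 76 on 416–426. None is affected.
- The 4-week visit after topical rescue started on day 113: 113 + 28 = 141, so days 136–146. If the Week 32 visit itself moves by ±5, the range is 131–151. Days 142–151 of that range are in the gap.
- The same visit after topical rescue at Week 64: 337 + 28 = 365, range 355–375. It does not reach the overlap.
- Premature-discontinuation and unscheduled visits can fall on any day, so they can reach both.

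**When a gap visit changes a result.** A visit on days 142–155 is 169 − 142 = 27 to 169 − 155 = 14 days from the Week 40 nominal day. An on-time Week 40 visit is at most 5 days away and would be chosen even with the corrected window. The error therefore matters mainly when the gap visit is the subject's only assessment in days 142–211. For that subject:

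- As-observed: the Week 40 EASI, SCORAD, IGA, BSA and PGIS values are lost.
- Vital signs: SAP 11.4.2 summarises change at post-baseline visits and safety data are not imputed, so the Week 40 value is lost.
- NRI (SAP 10.1.5): having no evaluation in the window makes the subject a non-responder unless a responder both before and after it. A responder at the gap visit who does not return is counted as a non-responder at Week 40.
- LOCF (SAP 10.1.5): the most recent earlier non-missing value is carried. The SAP does not say whether a value outside every window qualifies. If it does not, the Week 32 value is used at Week 40, and for a subject who never returns also at Weeks 52, 64, 76 and 88.

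**The case against.** The best defence is that the slip has little to act on, and most of that stands.

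- A reader might infer that the visit after topical rescue, where continuation on study drug is decided, loses its EASI and IGA. SAP 10.1.5 already excludes efficacy assessments after the first dose of rescue, 30 mg or topical, from NRI, LOCF and as-observed results. The stopping decision is made at the site from the EASI score, not from an analysis window. The separate rescue summary in SAP 10.5 states no method or windows, so distortion there cannot be shown.
- A reader might infer a general loss of Period 2 laboratory data. SAP 11.3.2.1 plans by-visit laboratory means for Period 1 only, and shift, extreme-value and potentially significant summaries use all treatment-emergent values. A by-visit loss arises only if the broader wording of protocol 8.1.6.3 is followed.
- Since 14 of the 55 days between the two nominal days have no window, a reader might infer that a quarter of discontinuation visits in that interval are lost. This would need visits spread evenly and no later attendance. The protocol asks subjects who stop study drug to keep attending, and an on-time Week 40 visit supersedes the gap visit.
- Protocol 8.1.5 already makes subjects non-responders in NRI once study drug is discontinued, so the NRI effect is new only under the SAP's wording, which omits that rule.
- Time to loss of EASI 50 response is not shown to be affected: SAP 10.1.3 computes time-to-event variables from event dates.

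The objection does not rescue the table. The number 378 recurs in Tables 9 and 10 while Table 8 has 380, so a text-extraction fault is unlikely. A start of 156 would follow if a site visit existed at Week 36 (day 141), because (141 + 169)/2 = 155; none is scheduled, and that origin is only a guess. SAP 12.1 declares no departure from the window rule.

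**Conclusion.** Wrong as written, with limited impact. Fourteen days have no window in Table 7, and two days have two windows in Tables 7, 9 and 10. The arithmetic is certain; it rests only on the SAP's nominal days, its midpoint rule and its worked example.

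The practical exposure is narrow: mainly a premature-discontinuation or unscheduled visit in the gap with nothing else in days 142–211 and, for efficacy, no earlier rescue. The documents give no basis for counting such subjects, so no percentage should be attached. The direction of any bias is not established either, since subjects may stop for reasons other than worsening disease. Period 2 efficacy is descriptive (SAP 10.1), and the Week 16 primary analysis uses Period 1 windows that this error does not touch.

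**What to change.** - Table 7: change the Week 40 interval to 142–211.
- Tables 7, 9 and 10: change the Week 76 interval to 380–463, matching Table 8.
- SAP 6.0: reword the tie sentence to agree with its own example, so that the split day goes to the earlier visit. All the other interior boundaries of Table 7 already follow that convention.

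This costs four table cells and one sentence, and it changes no assignment of an on-schedule visit. It restores a single visit for every day in the windowed range, and with the Week 40 gap closed the LOCF question above no longer arises for days 142–155.

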**Table 8. Analysis Windows for Daily Pruritus NRS, ADerm-SS, and ADerm-IS (Period 2)**

Scheduled Week	Nominal Day	P2 Rx Day Interval
Entry of Period 2 (Week 16)	1	< 1 a
Week 17	8	2 – 11
Week 18	15	12 – 18
Week 19	22	19 – 25
Week 20	29	26 – 32
Week 21	36	33 – 39
Week 22	43	40 – 46
Week 23	50	47 – 53
Week 24	57	54 – 60
Week 25	64	61 – 67
Week 26	71	68 – 74
Week 27	78	75 – 81
Week 28	85	82 – 88
Week 29	92	89 – 95
Week 30	99	96 – 102
Week 31	106	103 – 109
Week 32	113	110 – 116
Week 33	120	117 – 123
Week 34	127	124 – 130
Week 35	134	131 – 137
Week 36	141	138 – 144
Week 37	148	145 – 151
Week 38	155	152 – 158
Week 39	162	159 – 165
Week 40	169	166 – 211
Week 52	253	212 – 295
Week 64	337	296 – 379
Week 76	421	380 – 463
Week 88	505	464 – 546

a. ADerm-IS CCI assessments collected on or before Day 1 of Period 2 will be used as entry of Period 2 (P2 Rx Day Interval:  $\leq 1$ ).

**Table 9. Analysis Windows for DLQI (Period 2)**

Scheduled Week	Nominal Day	P2 Rx Day Interval
Entry of Period 2 (Week 16)	1	≤ 1
Week 40	169	2 – 211
Week 52	253	212 – 295
Week 64	337	296 – 379
Week 76	421	378 – 463
Week 88	505	464 – 546

**Table 10. Analysis Windows for MOS, and POEM (Period 2)**

Scheduled Week	Nominal Day	P2 Rx Day Interval
Entry of Period 2 (Week 16)	1	≤ 1
Week 24	57	2 – 113
Week 40	169	114 – 211
Week 52	253	212 – 295
Week 64	337	296 – 379
Week 76	421	378 – 463
Week 88	505	464 – 546

**Table 11. Analysis Windows for Asthma Symptoms Questionnaire and Daytime Nasal Symptoms Questionnaire (Period 2)**

Scheduled Week	Nominal Day	P2 Rx Day Interval
Entry of Period 2 (Week 16)	1	≤ 1
Week 40	169	2 – 336

**Table 12. Analysis Windows for Blood Sample Parameters\* (Period 2)**

Scheduled Week	Nominal Day	P2 Rx Day Interval
Entry of Period 2 (Week 16)	1	≤ 1
Week 20	29	2 – 56

\* Including T (CD4+ and CD8+) cells, B (CD19+) cells, natural killer (NK) cells, and natural killer-T (NKT) cells.

### **Dealing with Multiple Measurements Collected on the Same Day**

For efficacy related analyses, if there are multiple measurements for a particular parameter collected on the same day for the same subject, the most conservative measurement indicating the worst disease status will be used in the analyses.

For safety related analyses, if there are multiple measurements made for a particular laboratory or vital sign parameter on the same day for the same subject without the actual times, the average of the values will be used in the mean change analyses. For summaries and listings for shift from baseline on the minimum, maximum, final, and potentially significant values, all collected values within the defined treatment-emergent window will be used.

### **Definition of Missing Data Imputation**

No global imputation is taking place at the database level. Efficacy related imputations are outlined in Section 10.1.5. There is no imputation for missing values in the safety analyses.

## **7.0 Demographics, Baseline Characteristics, Medical History, and Previous/Concomitant Medications**

### **7.1 Demographic and Baseline Characteristics**

Demographics and Baseline characteristics will be summarized for each arm and for overall of the ITT populations. Continuous variables will be summarized with the number of non-missing observations by mean, standard deviation, first quartile, median, third quartile, minimum and maximum values. Categorical data will be summarized using frequencies and percentages.

The following demographic and baseline parameters will be summarized.

#### **Subject Demographics**

- Sex (Male, Female)
-

- Age (years), defined as the number of years from year of birth to year of first dose of study drug
- Age categories (< 40 years, 40 – 65 years, ≥ 65 years)
- Race (White, Black, American Indian/Alaska Native, Native Hawaiian or Other Pacific Islander, Asian, Other)
- Ethnicity (Hispanic or Latino, not Hispanic or Latino)
- Body weight (kg)
- Height (cm)
- BMI (kg/m^2)
- BMI category (< 25, ≥ 25 – < 30, ≥ 30 – < 40, ≥ 40)
- Geographic Region (US/PR/Canada, EU/AUS, Japan)

#### **Tobacco/Nicotine and Alcohol Use**

- Tobacco/Nicotine Use (unknown, never, current, former)
- Alcohol Use (unknown, never, current, former)

#### **Baseline Characteristics**

- EASI overall score and body region scores
  - Investigators Global Assessment (IGA)
  - Body Surface Area (BSA) in percentage
  - Scoring Atopic Dermatitis (SCORAD)
  - Dermatology Life Quality Index (DLQI)
  - Daily pruritus Numerical Rating Scale (NRS)
  - Patient Global Impression of Severity (PGIS)
  - Atopic Dermatitis Symptom Scale (ADerm-SS)
  - Atopic Dermatitis Impact Scale (ADerm-IS)
  - Medical Outcomes Study (MOS) Sleep Scale
  - Patient Oriented Eczema Measure (POEM)
  - Asthma Symptoms and Daytime Nasal Scores (subjects with symptoms)
-

- Actigraphy data: total sleep time per night (TST min), Sleep Efficiency (%), Wake After Sleep Onset (WASO), number of scratching events per hour, mean activity during rest (sleep)
- Disease duration since diagnosis (years)
- Disease duration since symptoms started (years)
- Duration between symptoms and diagnosis (years)
- Prior Atopic Dermatitis Treatment
- Electrocardiogram (ECG), containing categories including normal, abnormal – not clinically significant, abnormal – clinically significant, unable to evaluate, and details of the abnormality when applicable.
- TB Status: Tuberculin PPD skin test result, QuantiFERON-TB Gold test result
- Chest x-ray
  - Normal, Abnormal
  - Calcified granulomas (Absent, Present)
  - Pleural scarring (Absent, Present)
  - Pleural thickening (Absent, Present)

## 7.2 Medical History

For the ITT\_1 population, the medical history data will be summarized and presented using body systems and conditions/diagnoses as captured on the CRF. The body systems will be presented in alphabetical order and the conditions/diagnoses will be presented in alphabetical order within each body system. The number and percentage of subjects with a particular condition/diagnosis will be summarized for each treatment group. Subjects reporting more than one condition/diagnosis within a body system will be counted only once for that body system. If no subject reported information for a specific body system, then that category will not be displayed in the summary table.

## 7.3 Previous Treatment and Concomitant Medications

Prior and concomitant medications will be summarized by generic name. A prior medication is defined as any medication taken prior to the first dose of study drug. A

---

concomitant medication is defined as any medication that started prior to the first dose of study drug and continued to be taken after the first dose of study drug or any medication that started after the first dose of study drug, but not after the last dose of study drug. The number and percentage of subjects who had taken medications will be summarized by generic drug name assigned by the World Health Organization (WHO) for both prior and concomitant medications.

#### **7.4 Protocol Deviations**

Number and percentage of subjects who reported at least one of the following protocol deviation categories will be provided.

- Subject entered into the study even though she/he did not satisfy entry criteria
- Subject who developed withdrawal criteria during the study and was not withdrawn
- Subject who received wrong treatment or incorrect dose
- Subject who received excluded or prohibited concomitant treatment

#### **8.0 Patient Disposition**

The number of subjects for each of the following categories will be summarized, for overall and for each treatment group in the ITT\_1 Population:

- Number of subjects randomized to Period 1
- Number of subjects treated in Period 1
- Number of subjects who completed Period 1
- Number of subjects who discontinued study drug during Period 1
- Number of subjects who prematurely discontinued from Period 1

The number of subjects for each of the following categories will be summarized, for overall and for each treatment group in the ITT\_2 Population:

- Number of subjects re-randomized to Period 2
-

- Number of subjects treated in Period 2
- Number of subjects who completed Period 2
- Number of subjects who discontinued study drug during Part Period 2
- Number of subjects who prematurely discontinued from Period 2

In addition, the reasons (primary and all reason) for premature discontinuation of study drug and discontinuation from the study will be summarized with frequencies and percentages.

